Approximately 15 participants, including a minimum of 7 with a non-bone metastatic lesion that can be biopsied, will be enrolled in each immunotherapy combination cohort in Stage 1. Enrollment of participants in each cohort may occur simultaneously. An additional approximately 15 participants, including a minimum of 7 with a non-bone metastatic lesion, will be enrolled in Stage 2, if the cohort is expanded.

The duration of immunotherapy combination study intervention will be dependent on the combination administered and will continue for the duration described in the cohort appendix for each respective combination, unless the participant is no longer clinically benefiting (as evidenced by symptomatic or radiographic disease progression and/or clinical deterioration); experiences any toxicity meeting specified discontinuation criteria (as described in the cohort appendix for each respective combination) or unacceptable toxicity in the best clinical discretion of the treating physician; reaches the maximum duration of study intervention; or withdraws consent. Participants will be followed for up to 2.5 years from the time of the initiation of study intervention. Depending on the combination administered, participants who are clinically benefiting, as defined by the Investigator at the end of the study treatment period, may have post-study access to the immunotherapy combination received during the study after agreement from the Medical Monitor.

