6.5.2 Prohibited Therapy

The medications listed below are prohibited during the study. The Sponsor must be notified if a participant receives any of these during the study.

- Any concurrent systemic chemotherapy, immunotherapy, biologic, hormonal treatment or radiotherapy (except palliative radiotherapy) not specified in this protocol or subsequent amendments. Concurrent use of hormones for noncancer-related conditions are permitted.
 - Exception: Androgen deprivation therapy. Participants are required to maintain castrate-level testosterone (< 50 ng/dL) with a gonadotropin-releasing hormone (GnRH) agonist or antagonist ± antiandrogen. Participants without history of bilateral orchiectomy are required to remain on ADT.
- Any concurrent investigational anticancer therapy not specified in this protocol or subsequent amendments.
- Anti-CTLA-4, anti-PD-L1, or anti-PD-1 agents through 100 days after the last dose of study intervention, except for agents that are not part of the immunotherapy combinations.
- Immunosuppressive medications at chronic systemic doses > 10 mg/day prednisone (or equivalent) within 28 days before the first dose (note: hormone replacement therapy (HRT), such as thyroxine, insulin, or physiologic corticosteroid replacement therapy ≤ 10 mg of prednisone/day for adrenal or pituitary insufficiency, etc. is not considered a form of systemic treatment). A temporary course of steroids (ie, contrast allergy, chronic

obstructive pulmonary disease) may be permitted, depending on the duration and dose, after discussion and agreement with the Medical Monitor.

- Live attenuated vaccines within 30 days prior to the first dose of study intervention and through 180 days after the last dose of study intervention. Examples of live vaccines include, but are not limited to, the following: measles, mumps, rubella, varicella/zoster, yellow fever, rabies, bacille Calmette-Guerin (BCG), and typhoid vaccine.
- Any botanical preparation (eg herbal supplements or traditional Chinese medicines) intended to treat the disease under study. Use of marijuana and its derivatives for treatment of symptoms related to cancer or to cancer treatment are permitted.

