6.7 INTERVENTION AFTER THE END OF THE STUDY

Participants who are clinically benefiting as defined by the Investigator at the end of the study may have post-study access to the immunotherapy combination after agreement from the Medical Monitor.

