7 DISCONTINUATIONS OF STUDY INTERVENTION AND PARTICIPANT DISCONTINUATION/WITHDRAWAL

7.1 DISCONTINUATION OF STUDY INTERVENTION

Participants must discontinue study intervention if they experience any of the following:

- Intolerable toxicity related to study intervention, including the development of an adverse event (AE) determined by the Investigator to be unacceptable even with the participant's potential response to intervention due to the severity of the event
- Any medical condition that may jeopardize participant safety if he continues to receive the study intervention
- Use of another anticancer therapy (see [Section 6.5.2](#) and as described in the cohort appendix for each respective combination, as applicable)
- Symptomatic deterioration attributed to disease progression

- Progression of disease: Either unequivocal symptomatic progression necessitating a change in therapy in the opinion of the treating physician or confirmed radiographic progression as defined by cross-sectional imaging per PCWG3-modified RECIST 1.1 (see [Appendix 3](#)) in the absence of clinical benefit (refer to [Section 4.4](#)).

Participants have the right to voluntarily withdraw from study intervention at any time for any reason. In addition, the Investigator has the right to withdraw a participant from study intervention at any time. Reasons for withdrawal from the study intervention may include, but are not limited to, the following:

- Investigator or Sponsor determines it is in the best interest of the participant
- Participant noncompliance

The primary reason for study intervention discontinuation should be documented on the appropriate eCRF page.

The visit at which disease assessment shows progressive disease (PD) may be used as the treatment discontinuation visit if it occurs within 28 (± 7) days after the last dose of study intervention. Participants who discontinue study intervention for any reason other than PD or loss of clinical benefit should have an end of treatment discontinuation assessment as outlined in the SOA (see [Section 1.3](#)). All participants should continue follow-up as outlined in the SOA.

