8.3 ADVERSE EVENTS AND SERIOUS ADVERSE EVENTS

The definitions of an AE or SAE can be found in [Appendix 5](#).

Investigators will seek information on AEs at each participant contact until at least 100 days after the last dose of study intervention. AEs reported by the participant (or, when appropriate, by a caregiver, surrogate, or the participant’s legally authorized representative) or noted by study personnel, will be recorded in the participant’s medical record and on the Adverse Event eCRF page. If the AE is determined to meet seriousness criteria, the event will be reported as an SAE on the study-specific SAE Report Form (SAERF) within 24 hours of awareness. Seriousness criteria is defined in [Appendix 5](#).

The Investigator and any qualified designees are responsible for detecting, documenting, and recording events that meet the definition of an AE, AESI (as applicable), or SAE and remain responsible for following up AEs that are serious, considered related to the study intervention or study procedures, or that caused the participant to discontinue the study intervention (see [Appendix 5](#)).

8.3.1 Time Period and Frequency for Collecting AE, SAE, and Other Reportable Safety Event Information

All SAEs will be collected from the time the participant signs informed consent until at least 100 days after the last dose of study intervention. Prior to initiation of study intervention, only SAEs that are-related to a protocol-mandated intervention, including those that occur prior to the assignment of study procedures (eg, screening invasive procedures, such as biopsies) should be reported. After obtaining informed consent, but prior to initiation of study intervention, other medical occurrences will be recorded as medical history.

All AEs, including AESIs (as applicable), will be collected from the start of study intervention until at least 100 days after the last dose of study intervention.

If the Investigator learns of any SAE, including a death, at any time after the end of the AE reporting period, and he/she considers the event to be reasonably related to the study intervention or study participation, the Investigator must promptly notify the Sponsor or its designee. The Investigator should report these events directly to the Sponsor or its designee, either by faxing or emailing the SAERF.

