9.3.3.1 Pharmacokinetic Analysis

Sparse PK analysis may be performed evaluating trough levels for all biologic study intervention and maximum observed drug concentration (Cmax) for exploratory biologic study intervention (non-PD-1 agents) when possible.

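### Protocol 6.5.2, third bullet: the exception for checkpoint inhibitors is inverted, so from last dose to day 100 the core rule for this drug class points the wrong way

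*Protocol*

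**What the plan says.** The list in Protocol Section 6.5.2 opens: "The medications listed below are prohibited during the study". The sponsor must be told if a participant receives anything on it. Three bullets matter here.

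- Bullet 1 bars "Any concurrent systemic chemotherapy, immunotherapy, biologic, hormonal treatment or radiotherapy (except palliative radiotherapy) not specified in this protocol or subsequent amendments".
- Bullet 2 does the same for concurrent investigational anticancer therapy from outside the protocol.
- Bullet 3 covers anti-CTLA-4, anti-PD-L1 and anti-PD-1 "agents through 100 days after the last dose of study intervention, except for agents that are not part of the immunotherapy combinations".

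Other sections bear on how bullet 3 should be read.

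- Section 9.3.3.1 plans peak drug concentrations "for exploratory biologic study intervention (non-PD-1 agents) when possible", which implies that PD-1 agents are expected among the study drugs.
- Section 4.1 says that, depending on the combination, participants whom the investigator judges to be benefiting "at the end of the study treatment period, may have post-study access to the immunotherapy combination received during the study", with the Medical Monitor's agreement.
- Section 6.7 says that participants benefiting when the study ends "may have post-study access to the immunotherapy combination after agreement from the Medical Monitor".
- Section 7.1 makes "Use of another anticancer therapy" a mandatory reason to stop study intervention and refers the reader to Section 6.5.2.
- Under Section 8.3.1, adverse events "will be collected from the start of study intervention until at least 100 days after the last dose of study intervention". Their incidence and severity are the only primary endpoint (Section 3).

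**The concern.** A prohibition with an exception bans everything in the class except what the exception names. Bullet 3 names the agents outside the combinations, so what stays banned is the study's own agents. One would expect the opposite: outside checkpoint inhibitors kept away during treatment and washout, and the study's own left alone.

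This is an operative rule that sites follow. It determines what a participant may receive, what must be notified to the sponsor and, through the cross-reference in Section 7.1, part of the discontinuation logic. At stake is whether a site can tell from the core protocol if an outside checkpoint inhibitor is acceptable soon after the last dose, and if continued access to a study checkpoint inhibitor at that time counts as a violation.

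**Working it through.** The plan gives no figure on this point, so the check is one of logic and of setting sections side by side.

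**Step 1: evaluate the exception.**

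| Checkpoint inhibitor | Bullet 3 as written | Bullet 3 without 'not' |
|---|---|---|
| Part of a study combination | Prohibited | Exempt |
| Not part of a study combination | Exempt | Prohibited |

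Deleting one word reverses both rows.

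**Step 2: during treatment.** The bullets are separate prohibitions, so an exception inside bullet 3 limits bullet 3 only. An outside checkpoint inhibitor given alongside study drug is still barred by bullet 1 and, if investigational, by bullet 2. Section 7.1 also requires study intervention to stop if another anticancer therapy is used. The inversion therefore opens little while dosing continues.

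**Step 3: after the last dose.** Bullets 1 and 2 turn on the therapy being concurrent, which no longer clearly applies once dosing has ended. Bullet 3 is then the core protocol's only rule for this class with a stated time limit, and it exempts the outside agents. The period is 100 days: 100 / 7 = 14.3 weeks, or 100 / 30.44 = 3.3 months. Section 8.3.1 sets the same 100 days as the minimum for collecting adverse events after treatment.

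**Step 4: post-study access.** Section 4.1 judges benefit when the treatment period ends. Participants are followed for up to 2.5 years from the start of study intervention, so that moment can fall while the participant is still on study and within 100 days of the last dose. Bullet 3 as written would then bar a drug that Section 4.1 allows. Three conditions are needed: the combination contains a checkpoint inhibitor, the cohort offers access, and access starts before day 100.

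**Step 5: could the wording be deliberate?**

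- An exemption meant to free outside agents for next-line use would apply only after the last dose. This one has no such limit, and it would still leave the study's own agents as the banned ones.
- A ban on reusing study agents off study is conceivable, but it does not fit the access rule in Section 4.1.
- With 'not' removed, the bullet agrees with bullets 1 and 2 and with Section 4.1.

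**Step 6: effect on the statistics.** The two-stage rule rests on response rates of 10% and 25%, on 15 and 30 participants, and on thresholds of 2 and 6 responses. The exact intervals for adverse event rates depend only on counts and cohort size. Bullet 3 enters none of these calculations.

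**The case against.** The best defence is that this is a one-word slip that nobody would act on. No site would withhold a study drug because of bullet 3 when the cohort appendix directs that it be given. Bullets 1 and 2 still protect participants on treatment. Section 6.5 tells sites to ask the Medical Monitor about concomitant or prior therapy, and access under Section 4.1 needs the Medical Monitor's agreement. Sections 6.5.1 and 7.1 point to cohort appendices for combination-specific rules, and SAP Section 3.1 says the core protocol and appendix are to be used together.

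Most of this stands. It confines the gap to the time after the last dose and makes the practical effect uncertain. It does not make the rule correct: a query route does not repair a rule that gives the wrong answer, and the appendices cannot be checked here.

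A reader might infer more than the documents support, in four ways.

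- **That outside checkpoint inhibitors are allowed during treatment.** They are not. Bullet 3's exemption does not cancel bullets 1 and 2.
- **That bullet 3 directly conflicts with Section 6.7.** Section 6.7 applies once the study has ended, which Section 4.5 ties to the last participant's last visit or last required data point. The list in Section 6.5.2 applies during the study. Only Section 4.1 clearly leaves room for overlap.
- **That adverse event rates are distorted by a calculable amount.** The documents do not say how many participants would start an outside checkpoint inhibitor in the window, or have a new event after doing so. Events after any other next-line therapy would be counted in the same way.
- **That the SAP's definition of treatment-emergent events is therefore faulty.** Counting all events is a legitimate main analysis, SAP Section 5.5.2 already plans a treatment-related summary, and investigators must weigh other causes. An extra table would be a preference.

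**Conclusion.** The third bullet of Section 6.5.2 is wrong as written and should be corrected. The consequence is one of safety conduct: an unclear period of 100 days after the last dose, coinciding with the minimum adverse event window for the primary endpoint, and a conditional conflict with access under Section 4.1.

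The conclusion rests on two assumptions. The first is that some combinations contain a checkpoint inhibitor, which Section 9.3.3.1 implies. The second is that the cohort appendices, which were not available, do not already override the bullet. If they do, the core text is still wrong but the practical gap closes for those cohorts. No sample size, error rate, power figure or interval is affected.

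**What to change.** Delete 'not' from the exception in bullet 3, so that the exempt agents are those belonging to the immunotherapy combinations. Add in brackets that this means agents given as study intervention or as post-study access under Sections 4.1 and 6.7. Naming Section 4.1 matters because that is where the overlap can arise.

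The edit is one word and one bracket in the next protocol amendment. SAP Section 6 already announces an amendment, but only for differences in endpoints, so this item would have to be added. Cohort appendices should be checked for matching wording at the same time.

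The real cost falls on participants: outside checkpoint inhibitors are then clearly barred for up to 100 days after the last dose, which may delay that choice of next-line therapy. No new data collection and no change to the SAP are needed.

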6.6 DOSE MODIFICATIONS (ESCALATION/TITRATION/ OTHER)

Specific anticipated or potential toxicities associated with the administration of the study intervention, as well as the measures taken intended to avoid or minimize such toxicity in this trial, are described in the cohort appendix for each respective combination.

Refer to the Investigator's Brochure (IB) for the individual components of each combination for complete summaries of safety information.

6.7 INTERVENTION AFTER THE END OF THE STUDY

Participants who are clinically benefiting as defined by the Investigator at the end of the study may have post-study access to the immunotherapy combination after agreement from the Medical Monitor.

7 DISCONTINUATIONS OF STUDY INTERVENTION AND PARTICIPANT DISCONTINUATION/WITHDRAWAL

7.1 DISCONTINUATION OF STUDY INTERVENTION

Participants must discontinue study intervention if they experience any of the following:

- Intolerable toxicity related to study intervention, including the development of an adverse event (AE) determined by the Investigator to be unacceptable even with the participant's potential response to intervention due to the severity of the event
- Any medical condition that may jeopardize participant safety if he continues to receive the study intervention
- Use of another anticancer therapy (see [Section 6.5.2](#) and as described in the cohort appendix for each respective combination, as applicable)
- Symptomatic deterioration attributed to disease progression

- Progression of disease: Either unequivocal symptomatic progression necessitating a change in therapy in the opinion of the treating physician or confirmed radiographic progression as defined by cross-sectional imaging per PCWG3-modified RECIST 1.1 (see [Appendix 3](#)) in the absence of clinical benefit (refer to [Section 4.4](#)).

Participants have the right to voluntarily withdraw from study intervention at any time for any reason. In addition, the Investigator has the right to withdraw a participant from study intervention at any time. Reasons for withdrawal from the study intervention may include, but are not limited to, the following:

- Investigator or Sponsor determines it is in the best interest of the participant
- Participant noncompliance

The primary reason for study intervention discontinuation should be documented on the appropriate eCRF page.

The visit at which disease assessment shows progressive disease (PD) may be used as the treatment discontinuation visit if it occurs within 28 (± 7) days after the last dose of study intervention. Participants who discontinue study intervention for any reason other than PD or loss of clinical benefit should have an end of treatment discontinuation assessment as outlined in the SOA (see [Section 1.3](#)). All participants should continue follow-up as outlined in the SOA.

7.2 PARTICIPANT DISCONTINUATION/WITHDRAWAL FROM STUDY

The total length of study participation, from participant screening to the end of study, is expected to be approximately 31 months.

When study intervention is discontinued, participants should have an end of treatment discontinuation assessment followed up by an assessment 14-28 days after the last dose of study intervention as outlined in the SOA (see [Section 1.3](#)). Information on survival follow-up and new anticancer therapy will be collected every 3 months for up to 2.5 years from the initiation of study intervention until any of the following occurs:

- Death
- Loss to follow-up
- Study termination by the Sponsor
- Participant requests to be withdrawn from follow-up

A participant may withdraw consent at any time and discontinue study intervention and further participation in the study. This request must be documented in the source documents and signed by the Investigator. The Sponsor may retain and continue to use any data collected before such withdrawal of consent. Participants who withdraw consent will not be followed for any reason after consent has been withdrawn. However, the study staff may use a public information source (eg, county records) to obtain information about survival status only.

Other reasons for discontinuation of study intervention and/or participation in a follow-up phase of the study may include death, AEs, physician decision, protocol deviation, eligibility not met, progressive disease. A participant is considered to have completed all phases of the study as defined in the cohort appendix for each respective combination, including the lead-in phase, as applicable, the treatment phase, and the safety and survival follow-up after last dose of study intervention.

The primary reason for withdrawal from study should be documented on the appropriate eCRF page.

7.3 LOST TO FOLLOW-UP

A participant will be considered lost to follow-up if he repeatedly fails to return for scheduled visits and is unable to be contacted by the study site.

The following actions must be taken if a participant fails to return to the clinic for a required study visit:

- The site must attempt to contact the participant and reschedule the missed visit as soon as possible and counsel the participant on the importance of maintaining the assigned visit schedule and ascertain whether or not the participant wishes to and/or should continue in the study.
- Before a participant is deemed lost to follow-up, the Investigator or designee will make every effort to regain contact with the participant (where possible, 3 telephone calls and, if necessary, a certified letter to the participant's last known mailing address or local equivalent methods). These contact attempts should be documented in the participant's medical record or study file.
- Should the participant continue to be unreachable, he will be considered to have withdrawn from the study.

8 STUDY ASSESSMENTS AND PROCEDURES

Please see [Section 1.3](#) for the schedule of activities and procedures to be performed during the study. All activities should be performed and documented for each participant in the order of the SOA. Participants will be closely monitored for safety and tolerability throughout the study.

Participants should be assessed for toxicity prior to each dose; dosing will occur only if the clinical assessment and local laboratory test values are acceptable as deemed by the Principal Investigator (PI).

If the timing of a protocol-mandated study visit coincides with a holiday, weekend, or other administrative disruption that precludes the visit, the visit should be scheduled on the nearest feasible date. The time between doses must not be less than described in the cohort appendix for each respective combination.

Collection of any non-safety-related data or participant samples may be terminated by the Sponsor at any time if further collection of such data or samples is also not related to the study's primary or secondary objectives. The decision to discontinue any data collection will be communicated to the sites and Institutional Review Board/Independent Ethics Committee (IRB/IEC) by means of a memorandum and will not require a protocol amendment.

